7.7 Method of Subject Assignment to Treatment Groups

The study is a single arm, non-randomized trial. Patients will first be allocated to Phase I dose escalation cohorts at each dose level listed in Table 7.5. Patients will be enrolled and allotted to the next available opening for each dose cohort as specified. For the Phase II dose expansion cohort, all patients will be enrolled at the recommended phase II dose.

7.8 Preparation and Administration of Study Drug

Duvelisib

Duvelisib is provided in capsules with no additional preparation. The drug will be stored at the investigational pharmacy and dispensed to the patient. The medication can be taken with or without food. If a dose is missed by less than 6 hours, the dose should be taken immediately. If it has been more than six hours, the dose will be skipped and the next dose will be taken at the scheduled time.

Nivolumab

Nivolumab will be prepared per package insert by pharmacy staff. Nivolumab vial is diluted with either 0.9% sodium chloride solution or 5% dextrose for a final concentration not to exceed 10mg/mL or less than 1mg/mL in a volume less than or equal to 160mL. Dilutions will be made within 8 hours of infusion. Nivolumab will be administered by infusion over 30 minutes using a non-pyrogenic, low protein binding-in line filter.

7.9 Subject Compliance Monitoring

Compliance with duvelisib will be monitored with pill count at each 4-week visit. Patients will also be provided a pill drug diary (see Appendix B) to record pills taken, missed pills, damaged pills or other issues. This will be reviewed by the CRC at each visit. If there is significant non-compliance across multiple visits that is not due to adverse effects or other reasonable events, patient will be discontinued from the study. This will ultimately be at the discretion of the investigator (in discussion with the treating physician as appropriate).

7.10 Prior and Concomitant Therapy

7.10.1 Prohibited and/or Restricted Treatments

- Duvelisib is metabolized by CYP3A4
 - Medications and foods that are strong CYP3A inducers will decrease the area under the curve (AUC) of duvelisib and should therefore be avoided.
 - Medications that are strong CYP3A inhibitors will increase the AUC of duvelisib and should be avoided. If unavoidable, the investigator may permit dose reduction of duvelisib to 15mg BID in cases when there is no alternative to a concurrent CYP3A inhibitor.
 - Medications that are substrates for CYP3A that are co-administered with duvelisib should also be avoided as the exposures to these medications may increase in presence of duvelisib. Investigator should consider decreasing doses of these substrates as appropriate.
 - Ultimately dose adjustments and medication adjustments are at the discretion of the investigator.
 - See Appendix A for a list of medications
- Immunosuppressive agents unless they are utilized to treat an AE
- Concurrent administration of any anticancer therapies (investigational or approved) with the exception of subjects in the survival period of the study
- Use of allergen sensitization therapy
- Use of recreational drugs other than alcohol or tobacco. Marijuana for medical use is permitted.
- Palliative radiation treatment is not recommended while on combination therapy. If radiation is deemed necessary, duvelisib should be held for 1 week prior and 2 weeks after therapy. Any radiation-related AEs should resolve to grade 1 or less prior to resuming treatment.

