7.5 Treatment Regimen

Duvelisib

Duvelisib is available in 15mg and 25mg dose capsules. Based on information provided in the Investigators Brochure from SecuraBio, in Phase I trials with duvelisib as monotherapy for lymphoma, the maximum tolerated dose of duvelisib was 75mg BID²⁰. After further evaluation 25mg BID was chosen to be the preferred therapeutic dose in an effort to minimize toxicity without compromising efficacy. Given that duvelisib acts primarily as an immunomodulator, as opposed to being directly cytotoxic to tumor, doses were chosen to maximize T cell proliferation according to pre-clinical data²¹. These data suggest that doses lower than even 25mg BID may result in serum drug concentrations able to optimize T cell proliferation. Thus, doses lower than 25mg BID may be ideal for both maximizing immune changes in the TME and reducing patient toxicities. If significant toxicity is noted in the first 3 patients of each/any dose level, subsequent patients may be treated with a 2 week lead-in of duvelisib as monotherapy prior to the addition of nivolumab.

Dosing for the dose escalation phase will be as follows:

Table 7.5 Duvelisib Dose levels

Dose Level	Duvelisib Dose
Level I	15mg Daily
Level II	25mg Daily
Level III	25mg BID

Nivolumab

Nivolumab will be administered at a flat dose of 240mg every 2 weeks for the first 4 cycles, thereafter it then may be switched to 480mg every 4 weeks (+/- 1 week allowed without study deviation) if deemed appropriate by the treating physician in consultation with a given patient and his/her caretakers. Patients changed to the every 4 weeks schedule for nivolumab will continue to undergo close monitoring by the study team for potential toxicities, as deemed necessary and appropriate by the treating physician.

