7.6 Dose Adjustments and Adverse Reaction Management

Dose adjustments for toxicity of duvelisib and nivolumab are detailed below and are excerpted from the duvelisib package insert and the nivolumab package insert^{11,22}. Where appropriate, management guidelines for immune-related adverse events in patients receiving immune checkpoint therapy, from the American Society of Clinical Oncology (ASCO) Practice Guidelines has been included²³. The table below is not comprehensive and clinicians should refer to the ASCO Practice Guidelines for more detailed management recommendations. When possible, biopsies should be pursued to help determine the study drug(s) responsible for a given toxicity.

Table 7.6 Dose Adjustments for Toxicity

Toxicity	Adverse Reaction Grade	Recommended Management
Nonhematologic Adverse Reactions		
Infections	Grade 3 or higher infection	
Duvelisib
 
 - Withhold duvelisib until resolved - Resume at the same or reduced dose 
Nivolumab
 
 - Withhold nivolumab until resolved - Resume at same dose
	Clinical CMV infection or viremia (positive PCR or antigen test)	
Duvelisib
 
 - Withhold duvelisib until resolved - Resume at the same or reduced dose - If duvelisib is resumed, monitor patients for CMV reactivation by PCR or antigen test at least monthly

Toxicity	Adverse Reaction Grade	Recommended Management
		
Nivolumab
 
 - Withhold nivolumab until resolved - Resume at same dose
	PJP	
Duvelisib
 
 - For suspected PJP, withhold duvelisib until evaluated - For confirmed PJP, discontinue duvelisib 
Nivolumab
 
 - Withhold nivolumab until resolved
Non-infectious diarrhea or colitis	Mild/moderate diarrhea (Grade 1-2, up to 4 stools per day over baseline) and responsive to antidiarrheal agents, OR Asymptomatic (Grade 1) colitis	
Duvelisib
 
 - No change in dose - Initiate supportive therapy with antidiarrheal agents as appropriate - Monitor at least weekly until resolved 
Nivolumab
 
 - Continue nivolumab or hold until symptoms resolve

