Neutropenia	Absolute neutrophil count (ANC) 500 to 1000 cells/µL	
Duvelisib
 
 - Maintain duvelisib dose - Monitor ANC at least weekly 
Nivolumab
 
 - Withhold nivolumab until resolved if it is felt to contribute to the neutropenia, and otherwise continue nivolumab as previously - Resume at same dose
	ANC less than 500 cells/µL	
Duvelisib
 
 - Withhold duvelisib

Toxicity	Adverse Reaction Grade	Recommended Management
		
 - Monitor ANC until > 500 cell/uL - Resume duvelisib at same dose (first occurrence) or at a reduced dose for subsequent occurrence 
Nivolumab
 
 - Withhold nivolumab until resolved if it is felt to contribute to the neutropenia, and otherwise continue nivolumab as previously - Resume at same dose 
*If concern for auto-immune neutropenia, then hold nivolumab and follow practice guidelines

Thrombocytopenia	Platelet count 25K to < 50K cells/ μ L (Grade 3) with Grade 1 bleeding	
Duvelisib
 
 - No change in dose - Monitor platelet counts at least weekly 
Nivolumab
 
 - Withhold nivolumab until resolved - Resume at same dose
	Platelet count 25K to < 50K cells/ μ L with grade 2 bleeding OR platelet count <25K cells/ μ L (Grade 4)	
Duvelisib
 
 - Withhold duvelisib - Monitor platelet count until > 25K cells/uL and resolution of bleeding if applicable. - Resume duvelisib at same dose (first occurrence) or resume at a reduced dose for subsequent occurrence 
Nivolumab
 
 - Withhold nivolumab until resolved - Resume at same dose 
*If concerned for autoimmune thrombocytopenia, hold nivolumab and follow practice guidelines

Table 7.7 Dose Reductions for Duvelisib

Initial Dose	Decreased Dose
15mg Daily	None

25mg Daily	15mg Daily
25mg BID	25mg Daily

Note: If patient is on dose level 1, 15mg daily and has a dose interruption, duvelisib will be resumed at same dose. If patient subsequently requires another dose interruption at this level for the same toxicity, duvelisib should be discontinued. No more than 2 dose reductions for the same side effect are allowed for any patient, irrespective of starting dose.

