14.1. Phase I Portion of the Study

14.1.1. Study Design

The primary objectives of the phase I portion are to determine the maximum tolerated dose (MTD) of duvelisib when combined with anti-PD1 therapy nivolumab, and to decide on its recommended phase II dose (RP2D). Dose escalation will follow the decision rule in the following table, using the three dose levels defined in Section 7.5 (i.e., 15mg Daily, 25mg Daily, and 25mg BID), starting from the lowest dose. The MTD is defined to be the highest dose level at which no more than 1 of 6 treated patients experiences a DLT (DLT is defined in Section 8.1). Cohorts of three to six patients each will be treated at a dose level. Patients should have taken 75% of pills to be included in analysis of their respective cohort, as assessed through pill counts and pill diary. Only toxicities observed during the first treatment cycle will affect dose escalation. Late toxicities observed will be discussed at monthly data safety monitoring boards to determine if dose adjustments should be made.

After MTD is determined, we will decide on RP2D based on an overall consideration of DLT data, as well as immune cell profiling with laboratory correlates. For this purpose, our decision rule in the following table is a slight modification of the standard “3+3” to make sure 6 patients will be accrued at each safe dose in order to have enough patients for laboratory evaluations. RP2D should not be higher than MTD. If the MTD is not reached, RP2D will be decided based on safety data from acute and late toxicities as well as immune cell profiling data by the investigators (see section 13.1).

DECISION RULES FOR DOSE LEVEL ESCALATION

No. of patients with DLT's at this dose level	No. of patients treated at this dose level	Action
≤1	3	Treat 3 more patients at this dose level.
≤1	6	Treat 3 patients at the next higher dose level (or if at the highest level, stop the trial, and declare the dose at this level to be the MTD).

>1	3 or 6	Stop dose escalation. The previous dose is defined as MTD.
----	--------	--

Cohorts need not be completed if clear decisions can be made on the basis of an incomplete cohort. For example, if the first two patients in an intended cohort of three experience DLT's, escalation can be stopped without accruing the third member of the cohort.

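### The single inhibitor-adjusted dose in Section 7.10.1, 15mg BID, is a reduction only for patients currently taking 25mg BID and does not fit the two once-daily levels

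*Combined protocol and SAP*

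**What the plan says.** Section 7.10.1 sets the general rule: "Medications that are strong CYP3A inhibitors will increase the AUC of duvelisib and should be avoided". It then gives an exception, under which "the investigator may permit dose reduction of duvelisib to 15mg BID in cases when there is no alternative to a concurrent CYP3A inhibitor". The list closes with: "Ultimately dose adjustments and medication adjustments are at the discretion of the investigator". Nothing in the section ties 15mg BID to a particular level or current dose.

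The levels come from Section 14.1.1, which escalates "using the three dose levels defined in Section 7.5 (i.e., 15mg Daily, 25mg Daily, and 25mg BID), starting from the lowest dose". Section 7.5 adds that "Duvelisib is available in 15mg and 25mg dose capsules" and suggests that the best dose may lie below 25mg BID, so the recommended phase II dose could be a once-daily level.

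The other place where reduced doses appear is Section 7.6. It opens with "Dose adjustments for toxicity of duvelisib and nivolumab are detailed below" and contains "Table 7.7 Dose Reductions for Duvelisib". That table steps 25mg BID down to 25mg daily and 25mg daily down to 15mg daily, and gives no step below 15mg daily. Its note reads: "If patient is on dose level 1, 15mg daily and has a dose interruption, duvelisib will be resumed at same dose". A second interruption at that level for the same toxicity means stopping the drug. The dose of 15mg BID does not appear in the table.

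Section 4.2.4 excludes patients who used strong CYP3A inhibitors in the 2 weeks before study intervention.

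**The concern.** A dose adjustment for an inhibitor is meant to offset a rise in exposure. For a patient on either once-daily level, the one dose that Section 7.10.1 names is larger than the dose already being taken, so it cannot do that. An investigator treating such a patient has a figure in the protocol that does not apply and no figure that does. Patients at the same level could then be handled differently.

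The need can arise during treatment, after the entry exclusion has been met. Appendix A lists clarithromycin, several azole antifungals, diltiazem, verapamil and aprepitant as potent inhibitors, and Section 11.1 notes the boxed warning for infection with duvelisib. The gap is not confined to phase I, because the phase II dose may be once daily.

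**Working it through.** The plan gives no ratio or percentage for this adjustment, so there is no figure of its own to reproduce. The check is dose arithmetic.

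**Inputs.** Inhibitor-adjusted dose: 15mg BID (Section 7.10.1). Levels: 15mg daily, 25mg daily, 25mg BID (Sections 7.5 and 14.1.1). Toxicity steps: Table 7.7. Capsule strengths: 15mg and 25mg (Section 7.5).

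**Step 1: daily doses.** Daily dose = mg per dose × doses per day. The adjusted dose is 15 × 2 = 30 mg/day.

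**Step 2: ratio to the current dose.** Ratio = 30 / current daily dose.

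| Current dose | mg/day | Ratio | Change |
|---|---|---|---|
| 25mg BID | 25 × 2 = 50 | 30/50 = 0.60 | −20 mg/day |
| 25mg daily | 25 × 1 = 25 | 30/25 = 1.20 | +5 mg/day |
| 15mg daily | 15 × 1 = 15 | 30/15 = 2.00 | +15 mg/day |

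The 0.60 is the share of the dose that remains, which is a 40% cut.

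**Step 3: a patient already stepped down.** Table 7.7 takes 25mg BID to 25mg daily. Against the dose then being taken, 15mg BID is 30/25 = 1.20. A limit written by starting level would miss this patient; a limit written by current dose would not.

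**Step 4: carrying the same proportion down.** 0.60 × 25 = 15 mg/day, which is the existing Table 7.7 step. 0.60 × 15 = 9 mg/day, which 15mg and 25mg capsules cannot supply.

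**Step 5: exposure.** The documents give the direction of the AUC change but not its size. Assume, for illustration only, a multiplier m between 1.5 and 4 and exposure proportional to dose. Exposure relative to usual is ratio × m:

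- 25mg BID to 15mg BID: 0.60m = 0.9 to 2.4.
- 25mg daily to 15mg daily: 0.60m = 0.9 to 2.4.
- 25mg daily to 15mg BID: 1.20m = 1.8 to 4.8.
- 15mg daily to 15mg BID: 2.00m = 3 to 8.

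The mismatch in Step 2 does not depend on m. Whether a 60% dose is enough does depend on it.

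**Step 6: effect of a hold in cycle 1.** Sections 12.1 and 14.1.1 ask phase I patients to have taken 75% of their pills. If this is counted over the 28 once-daily doses of cycle 1 (the period is not stated, so this is an assumption), the minimum is 0.75 × 28 = 21 pills. A hold longer than 28 − 21 = 7 days would fall short.

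**The case against.** The strongest reply is that the clause permits a reduction, and a permission to reduce cannot be used to increase. On its natural reading it operates only at 25mg BID. Below that, the general rule still applies and the inhibitor is avoided. The investigator also has final say, so some variation between patients is accepted by design. Finally, although Table 7.7 sits among the toxicity rules, its title is general, and someone looking for a dose below 25mg daily would find 15mg daily there.

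Most of this stands. A reader might infer that the protocol directs an increase to 120% or 200% of the current dose. It does not: the wording is permissive, it speaks of reduction, and the same bullet warns that AUC rises. A reader might also treat the share of patients assigned to once-daily levels (12 of 18 in phase I if all three levels fill with 6 each) as the number at risk. It counts assignments. The documents give no basis for how many patients will need an unavoidable strong inhibitor, and the entry exclusion and the avoid rule both point to few.

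What the reply does not remove is the gap. If 15mg BID is meant only for 25mg BID, the text should say so, and it then offers no dose for the other two levels when avoidance has failed, which is the case the exception exists for. Table 7.7 helps only in part: its steps are introduced for toxicity, Section 7.10.1 does not refer to it, and it has no step below 15mg daily.

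**Conclusion.** The point holds as a gap in a patient-safety instruction. The ratios follow directly from the stated doses and need no assumption. The practical size is likely to be small and cannot be quantified from the documents. Endpoints, stopping boundaries and sample size do not turn on it. It is worth correcting because the stated dose is unsuitable at two of three levels and for patients already stepped down to 25mg daily, and because a sentence or two resolves it. The replacement doses proposed here rest on proportionality and on an existing step in the protocol, not on pharmacokinetic data, which the documents do not supply.

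**What to change.** In Section 7.10.1, word the exception by the dose the patient is currently taking:

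- On 25mg BID: 15mg BID may be permitted.
- On 25mg daily, whether assigned or reached under Table 7.7: reduce to 15mg daily.
- On 15mg daily: do not permit the strong inhibitor, or hold duvelisib while it is given.

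Add a cross-reference to Table 7.7, and have the sponsor's clinical team confirm the doses against the known size of the interaction.

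The cost is one short protocol edit. Dose levels, the DLT definition, the escalation table and the phase II rules stay as they are. The one side effect is in phase I: a hold during cycle 1 may leave a patient short of the pill requirement, and the cohort place would then need to be refilled. Given how rarely this should occur, that is a small price.

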7.10.2 Permitted therapy

- Inactivated influenza vaccination is permitted.
- Topical, ocular, intra-articular, intranasal and inhalational corticosteroids are permitted.
- Oral corticosteroids for premedication prior to scans are permitted.
- Systemic corticosteroids are permitted for treatment of AEs.
- Use of growth factors are permitted.
- Palliative care evaluation for symptom control can be offered to any patient on trial.
- For patients requiring surgery other than treatment-related biopsies, duvelisib should be held for 2 weeks before and after if possible. Duvelisib may be restarted sooner than 2 weeks, in consultation with the attending surgeon if the subject recovers and surgery-related AEs have decreased to grade 1 or baseline.

7.11 Blinding of Study Drug

This study consists of a single treatment arm, and therefore will not be blinded.

8.0 Safety and Adverse Events Assessing, Recording, and Reporting

An adverse event (AE) is defined as any new untoward medical occurrence or worsening of a pre-existing medical condition in a clinical investigation subject that does not necessarily have a causal relationship with this treatment. An AE can therefore be any unfavorable and unintended sign, symptom or disease temporally associated with study participation whether or not considered related to the investigational product.

The causal relationship to both/either study drug is determined by a physician and should be used to assess all adverse events (AE). The causal relationship can be one of the following:

- Unrelated: There is no temporal relationship to study drug; there is a reasonable causal relationship to another drug product, concurrent disease, or circumstance.
- Unlikely related: There is only a temporal relationship to study drug, but not a reasonable causal relationship between the investigational product and the AE.
- Possibly related: There is a reasonable possibility that the drug caused the adverse event. The investigator can provide a rationale or evidence to suggest a causal relationship between the study drug and the adverse event other than just a temporal relationship.
- Probably related: There is a reasonable causal relationship between the study drug and the AE, and/or the event responds to dechallenge.
- Definitely related: There is a reasonable causal relationship between the study drug and the AE. The event responds to withdrawal of investigational product (dechallenge), and recurs with rechallenge when clinically feasible.

8.1 Dose Limiting Toxicities

Acute dose limiting toxicities (DLTs) are defined as any of the following AEs and laboratory abnormalities considered possibly, probably, or definitely related to study treatment that occur any time from the initial dose of duvelisib in combination with nivolumab through day 28 of treatment. Toxicities occurring from day 29 through 28 days after completion of treatment will be considered late toxicities. Only acute DLTs will be considered for decisions to continue enrollment at the current dose level or proceed to the next dose level. Acute and late toxicities will be considered when deciding on the RP2D and will be discussed in monthly Data Safety Monitoring Board (DSMB) meetings. See Section 15.0 for further details.

Severity of adverse events will be graded by National Cancer Institute Common Terminology Criteria for Adverse Events version 5.0 (CTCAE v5.0). A goal of $\leq 33\%$ DLTs at each dose level will be considered acceptable.

Whenever possible, biopsies are recommended if they can be done safely to help determine between immune-related and other etiologies of toxicity, particularly for rash and colitis. Biopsies for elevated liver enzymes and/or for pneumonitis should be considered if deemed feasible and safe in the context of risk:benefit evaluation. General criteria for consideration of biopsy:

- Diarrhea/colitis
 - Biopsy proven grade ≥ 3 immune-related colitis
 - Diarrhea of grade ≥ 3 that does not respond to treatment with steroids within 5 days
- Pneumonitis
 - Immune-related pneumonitis grade ≥ 2

- Any grade ≥ 3 pneumonitis
- Hematologic abnormalities
 - Neutropenia grade 4 despite holding duvelisib for 7 days
 - Thrombocytopenia grade ≥ 3 with bleeding
 - Thrombocytopenia grade 4
- Other immune-related toxicities
 - Any grade ≥ 3 toxicity that does not respond to treatment within 5d
- For the remainder of non-hematologic toxicities, grade ≥ 3

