	Mild/moderate diarrhea (Grade 1-2, up to 6 stools per day over baseline) and unresponsive to antidiarrheal agents	
Duvelisib
 
 - Withhold duvelisib until resolved - Initiate supportive therapy with systemic steroids - Monitor at least weekly until resolved - Resume at a reduced dose - Gastroenterology consultation, recommend endoscopy and biopsy 
Nivolumab
 
 - Withhold nivolumab until resolved - Resume at same dose - Support with systemic steroids, gastroenterology consultation, recommend endoscopy and biopsy
	Abdominal pain, stool with mucus or blood, change in bowel habits, peritoneal signs, OR Severe diarrhea (Grade 3, >6 stools per day over baseline)	
Duvelisib
 
 - Withhold duvelisib until resolved - Initiate supportive therapy with enteric acting steroids (e.g., budesonide) or systemic steroids - Monitor at least weekly until resolved - Resume at a reduced dose

Toxicity	Adverse Reaction Grade	Recommended Management
		
 - For recurrent Grade 3 diarrhea or recurrent colitis of any grade, discontinue duvelisib 
Nivolumab
 
 - Withhold nivolumab until resolved - Resume at same dose - Systemic steroids, gastroenterology consultation and biopsy - If no improvement in 3-5 days, consider addition of infliximab
	Life-threatening, grade 4	
Duvelisib
 
 - Discontinue duvelisib 
Nivolumab
 
 - Permanently discontinue nivolumab - Systemic steroids, gastroenterology consultation and biopsy - If no improvement in 3-5 days, consider addition of infliximab
Cutaneous reactions	Grade 1	
Duvelisib
 
 - No change in dose - Initiate supportive care with emollients, antihistamines (for pruritus), or topical steroids - Monitor closely 
Nivolumab
 
 - Continue nivolumab - Support with topical emollients and/or mild-moderate potency topical corticosteroids
	Grade 2	
Duvelisib
 
 - Consider holding duvelisib, restart at same dose - Initiate supportive care with emollients, antihistamines (for pruritus), or topical steroids - Monitor closely 
Nivolumab
 
 - Consider holding nivolumab until resolved - Resume at same dose once improved to grade 1

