	Moderate (Grade 2) symptomatic pneumonitis	
Duvelisib
 
 - Withhold duvelisib - Treat with systemic steroid therapy - If pneumonitis recovers to Grade 0 or 1, duvelisib may be resumed at reduced dose - If non-infectious pneumonitis recurs or patient does not respond to steroid therapy, discontinue duvelisib 
Nivolumab
 
 - Withhold nivolumab until resolved to grade 0-1 - Resume at same dose - Prednisone 1-2mg/kg/d, with long taper - Consider pulmonology consultation, bronchoscopy and biopsy, empiric antibiotics - Monitor closely, if no improvement in 2-3 days treat as grade 3
	Severe (Grade 3) or Grade 4 life-threatening pneumonitis	
Duvelisib
 
 - Discontinue duvelisib - Treat with systemic steroid therapy 
Nivolumab
 
 - Permanently discontinue nivolumab - Treat with high dose IV steroids, consider infliximab, empiric antibiotics - Pulmonary and infectious disease consultations and biopsy if able
ALT/AST elevation	3 to 5 x upper limit of normal (ULN) (Grade 2)	
Duvelisib
 
 - Maintain duvelisib dose - Monitor at least weekly until return to < 3 x ULN

Toxicity	Adverse Reaction Grade	Recommended Management
		
Nivolumab
 
 - Withhold nivolumab until resolved to grade 1 - Resume at same dose - Consider steroids if abnormality persists and clinical symptoms
	> 5 to 20 × ULN (Grade 3)	
Duvelisib
 
 - Withhold duvelisib and monitor at least weekly until return < 3 × ULN - Resume duvelisib at same dose (first occurrence) or at a reduced dose for subsequent occurrence 
Nivolumab
 
 - Permanently discontinue nivolumab - Start steroids with methylprednisolone at 1-2mg/kg/d - Consider liver biopsy
	> 20 × ULN (Grade 4)	
Duvelisib
 
 - Discontinue duvelisib - Systemic steroid treatment 
Nivolumab
 
 - Permanently discontinue nivolumab - Start steroids with methylprednisolone at 1-2mg/kg/d - Avoid infliximab - Hepatology consultation, consider liver biopsy
Hematologic Adverse Reactions		

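### At Level II, a patient reduced from 25mg to 15mg daily in cycle 1 can still count as DLT-free at 25mg, because the 75% exposure rule counts capsules rather than dose

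*Combined protocol and SAP*

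**What the plan says.** **Events that drive escalation.** Section 8.1 counts related events that "occur any time from the initial dose of duvelisib in combination with nivolumab through day 28 of treatment". It adds that "Only acute DLTs will be considered for decisions to continue enrollment at the current dose level or proceed to the next dose level". The criteria go by type, grade and response to treatment; a reduction or hold is not among them. Grade 3 or higher diarrhea, for instance, is listed if it is one "that does not respond to treatment with steroids within 5 days". (The list stands under a sentence about when to biopsy. I read it as the DLT list, since the section has no other.)

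**Decision rule.** Section 14.1.1: "The MTD is defined to be the highest dose level at which no more than 1 of 6 treated patients experiences a DLT". With more than one DLT at a level, escalation stops and the previous dose becomes the MTD.

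**Exposure.** Section 14.1.1: "Patients should have taken 75% of pills to be included in analysis of their respective cohort". Section 12.1 repeats the 75% figure. Neither gives a denominator for a patient whose dose has changed. Section 14.1.2 defines evaluability differently: one dose of study drug is enough.

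**Reductions.** Table 7.6 has a row for "Mild/moderate diarrhea (Grade 1-2, up to 6 stools per day over baseline) and unresponsive to antidiarrheal agents", with the duvelisib instruction to withhold and then "Resume at a reduced dose". The rows for grade 3 diarrhea and grade 3 cutaneous reactions also lead to a reduced dose. For grade 2 pneumonitis, "If pneumonitis recovers to Grade 0 or 1, duvelisib may be resumed at reduced dose". Table 7.7 gives the steps: 25mg BID to 25mg daily, 25mg daily to 15mg daily, and none from 15mg daily.

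**The concern.** Section 7.6 and Section 8.1 use different lists. Some toxicities lead to a lower duvelisib dose without being DLTs:

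- grade 1-2 diarrhea that does not respond to antidiarrheals;
- grade 3 diarrhea that responds to steroids within 5 days and is not biopsy-proven immune-related colitis (diarrhea has its own item, so the clause for remaining toxicities does not reach it);
- grade 3 immune-related rash that responds within 5 days;
- grade 2 pneumonitis not judged immune-related, where the reduction is permitted rather than directed.

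If such a reduction falls in cycle 1, the rest of the DLT window is spent at a lower level. The 75% requirement ought to keep that patient from standing as evidence for the assigned level. At Level II it cannot. Tolerance of 15mg is then credited to 25mg, and the toxicity that prompted the reduction drops out of the count. At stake are whether Level III is opened and whether the MTD is put at Level II or above when Level I would have been the result.

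**Working it through.** **Inputs from the documents.** A 28-day window; capsules of 15mg and 25mg (Section 7.2); levels of 15mg daily, 25mg daily and 25mg BID (Table 7.5); reduction steps (Table 7.7); the 75% rule (Sections 12.1, 14.1.1); a limit of 1 in 6 (Section 14.1.1). The stated phase I maximum of 18 reproduces as 3 levels × 6. The documents give no operating characteristics for the escalation rule.

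**Step 1: the 75% rule by level.** Let d be days at full dose and h days held, leaving 28 − d − h days at the reduced dose.

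- *Level I.* There is no reduction step, so the issue does not arise.
- *Level II.* Capsules = d + (28 − d − h) = 28 − h, out of 28. The date of the reduction cancels out. The rule fails only if h exceeds 7 (h = 7 gives 21/28 = 75%).
- *Level III, with pills at the assigned dose as denominator.* Capsules = 2d + (28 − d − h) = 28 + d − h, out of 56, and 42 are needed, so d must be at least 14 + h. Reductions before 14 full-dose days are excluded, and time at the reduced dose is at most 14 − 2h days.

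**Step 2: one timeline at two levels.** Days 1-7 at full dose, days 8-12 held, days 13-28 reduced. The 5-day hold is an assumption.

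| Level | Capsules | mg | Passes 75% of capsules? |
|---|---|---|---|
| II | 7 + 16 = 23/28 = 82% | 7×25 + 16×15 = 415/700 = 59% | Yes |
| III | 14 + 16 = 30/56 = 54% | 30×25 = 750/1400 = 54% | No |

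The Level II patient spends 16 of 28 days (57%) at the Level I dose.

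**Step 3: a 75% rule in mg.** At Level II, 25d + 15(28 − d − h) ≥ 525 gives d ≥ 10.5 + 1.5h. With a 5-day hold, at least 18 full-dose days are needed, so the example patient would not qualify. At Level III every capsule is 25mg, so the mg rule equals the assigned-dose capsule count.

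**Step 4: effect on the decision.** One listed DLT in six escalates. If one of the other five is a patient of this kind and is scored as an event, the count is 2 in 6 and escalation stops. If that patient is replaced, the replacement decides.

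**Step 5: illustrative size.** Let p be the true cycle-1 rate of listed DLT or toxicity-driven reduction, and m the share of those patients who are reduced, have no DLT and are scored clean. Both are assumptions. A level passes with probability (1 − q)^6 + 6q(1 − q)^5, where q = p(1 − m) if they count as clean, q = p(1 − m)/(1 − pm) if they are replaced, and q = p if they are scored as events.

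| p | m | Counted clean | Replaced | Scored as event |
|---|---|---|---|---|
| 0.25 | 0.25 | 0.686 | 0.655 | 0.534 |
| 0.25 | 0.50 | 0.833 | 0.793 | 0.534 |
| 1/3 | 0.25 | 0.534 | 0.481 | 0.351 |
| 1/3 | 0.50 | 0.737 | 0.655 | 0.351 |
| 0.40 | 0.25 | 0.420 | 0.351 | 0.233 |
| 0.40 | 0.50 | 0.655 | 0.534 | 0.233 |

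**Step 6: effect on the MTD.** Assume p = 0.10, 0.25 and 0.40 at Levels I, II and III, with pass probabilities 0.886, 0.534 and 0.233. If a quarter of the Level II events are scored clean, the Level II figure becomes 0.686.

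| MTD | None scored clean | m = 0.25 at Level II only |
|---|---|---|
| Level I | 0.886 × 0.466 = 0.413 | 0.886 × 0.314 = 0.278 |
| Level II | 0.886 × 0.534 × 0.767 = 0.363 | 0.886 × 0.686 × 0.767 = 0.466 |
| Level III | 0.886 × 0.534 × 0.233 = 0.110 | 0.886 × 0.686 × 0.233 = 0.142 |

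**The case against.** Much can be said for the plan as it stands.

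- *Most serious toxicity is already listed.* Biopsy-proven grade 3 or higher immune-related colitis, immune-related pneumonitis from grade 2 and the remaining grade 3 or higher non-hematologic events are all in Section 8.1. This stands, and the gap is narrow.
- *The pill rule may be stricter than I read it.* If it means capsules of the assigned strength, the example patient took 7 of 28 and is excluded. The text does not say so. Holds over 7 days also fail the rule, and a hold until resolution may well last that long. Conversely, if the denominator is pills prescribed after the reduction, or if Section 14.1.2 governs, the Level III protection goes too.
- *Cycle-1 cases may be rare.* Section 11 gives median onsets of 3 months for infections and cutaneous reactions and 4 months for diarrhea and pneumonitis. That stands against any firm estimate, though the figures describe earlier duvelisib experience and not the combination with nivolumab.
- *There are later safeguards.* Level III is tested on its own six patients, and the RP2D weighs acute and late toxicities and may lie below the MTD. But these do not re-test Level II: if Level III fails, Section 14.1.1 makes the previous dose the MTD.
- *Scoring every reduction as an event would redefine the DLT.* It would also treat Level I differently, since a patient there resumes at the same dose. This stands, and is why the remedy works through exposure.

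A reader might infer that every level is affected, or that the protocol itself declares such a patient DLT-free. Neither holds: Level I cannot be reduced, Level III depends on the denominator, and the documents are silent on scoring.

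**Conclusion.** The gap is real and lies chiefly at Level II. There a patient can pass the 75% requirement with 59% of the planned dose and more than half the window at the Level I dose, and be counted as DLT-free at 25mg daily. The error runs only toward escalation, and with a limit of 1 in 6 one patient can be decisive. This rests on reading the rule as a plain capsule count, on a reduction in cycle 1 for a toxicity outside the Section 8.1 list, and on a hold of at most 7 days.

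The pass probabilities show direction and possible scale only, because the documents give neither p nor m. It would be tempting to conclude that the MTD or RP2D will be too high. The documents do not support that: they give no rate of cycle-1 reductions, the quoted onsets are mostly later, and the RP2D decision takes in more than acute DLTs. The change is still worth making, because a stated rule fails at a level where it is needed and the repair is small.

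**What to change.** Leave the dosing rules in Sections 7.6 and 7.7 and the DLT list in Section 8.1 as they are. Then:

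1. In Sections 12.1 and 14.1.1, define the 75% requirement as a share of the planned mg at the assigned level over cycle 1.
2. State that a patient without a DLT who falls below it because of a toxicity-driven reduction or hold is not one of the six DLT-free patients at that level. The sponsor should choose, before enrolment, between replacing the patient and scoring an event. Step 5 shows that replacement removes only part of the shift.
3. Reconcile these sections with the one-dose definition of evaluable in Section 14.1.2.
4. List cycle-1 reductions by assigned level at each escalation decision. A reduction late in the cycle can still leave a patient above 75% in mg, and this list makes it visible.

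The cost is a few sentences; pill counts and diaries already supply the data. Escalation becomes slightly more conservative, and an occasional patient may need replacing.
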